- Patient's satisfaction with the treatment process
- Pain assessment during the injection using a 11-point visual analogue scale
- Safety assessment of Embella® injectable solution

Study Method

It was a single group, before and after the clinical study. The study protocol as well as other essential documents (such as CRF, ICF, etc.) were approved by the Undersecretary of Research, Tehran University of Medical Sciences .

Also, all mentioned documents were approved by the ethics committee of Tehran University of Medical Sciences on 17 January 2023 (code: IR.TUMS.TIPS.REC.1401.102). The protocol was registered in the Iranian Registry of Clinical Trial Registry (IRCT) with registration number IRCT20190210042676N29.

Inclusion Criteria

- Age between 18 and 65 years old
- Individuals with any severity of unwanted submental fat
- Voluntarily signed the informed consent form and consented to the 3-month follow-up
- Willing to actively participate in the study and the scheduled visits

Exclusion Criteria

- Any previous interventions to treat SMF
- Anatomical features or previous trauma in the injection site which is liable to interfere with SMF evaluation or result in an aesthetically unacceptable outcome after treatment
- Evidence of any cause of submental enlargement other than SMF
- Patients with a body mass index (BMI) $> 30 \text{ kg m}^2$
- Those undergoing or considering a weight-reduction program
- Patients with a history of sensitivity to any components of the study medication or topical or local anesthetics
- Patients with a history of dysphagia
- Any inflammation, active infection, unhealed wound, or tissue scar at injection site
- Those using anticoagulants or NSAID or other medications that increase the risk of coagulation disorders within 7 days before injection
- Unrealistic expectations
- Pregnant or lactating women
- Those undergoing low sodium diets like hypertensive patients

Intervention

- Minimum 1 and maximum 3 treatment sessions (with at least 4 weeks intervals) with 2 ml of Embella® injectable solution, which contains 20 mg of DCA.
- 4 weeks after the first and second injections, the patient will be evaluated by the physician and research team. If necessary, they will receive additional injections; otherwise, they will proceed with post-injection follow-up.

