- The product is a 2 ml sterile, transparent, and colorless vial containing 20 mg of DCA. Additional ingredients include hyaluronic acid, water for injection, sodium chloride, sodium hydroxide, hydrochloric acid, and disodium phosphate anhydrous.
- Use of ice/cold packs, topical and/or injectable local anesthesia (e.g., lidocaine) may enhance patient comfort.

Method of administration

The product is indicated for subcutaneous administration only.

[figure not shown]
EMBELLA® is supplied in ready-to-use, single-use vials. Gently invert the vial several times before use. Do not dilute.

EMBELLA® shall be prepared for injections in the following way:

1. Remove the flip-off cap from the vial and clean the penetrable stopper of the vial with an antiseptic. If the vial, seal, or flip-off cap is damaged, do not use it.
2. Attach a large bore sterile needle to a sterile single-use 1 ml syringe.
3. Introduce the large bore sterile needle into the stopper of the vial and draw 1ml of EMBELLA® into the 1ml syringe.
4. Replace the large bore needle with a 30 gauge (or smaller)-0.5-inch needle. Expel any air bubbles in the syringe barrel before injecting the product into the subcutaneous fat.
5. To withdraw the remaining contents of the vial, repeat steps 3 and 4.

[figure not shown]
For injection, the needle is inserted perpendicular to the skin, and injection should be avoided in the area defined by a line 1 to 1.5 cm from the angle of the mandible to the mentum (Figure 1).

Figure 1. Avoid the Marginal Mandibular Nerve Area

[figure not shown]
Avoid injection into the platysma. Prior to each treatment session, palpate the submental area to ensure sufficient submental fat and to identify subcutaneous fat between the dermis and platysma (pre-platysmal fat) within the target treatment area (Figure 2).

Figure 2. Sagittal View of Platysma Area

Outline the planned treatment area with a surgical pen and apply a 1 cm^2 injection grid to mark the injection sites (Figures 3).

Figure 3. Injection Pattern

WARNINGS AND PRECAUTIONS

- Embella[®] should only be injected within the defined parameters. Each vial is intended for use in one patient and should be discarded after use.
- Store the product between 15°C and 30°C.
- Use of ice/cold packs, topical and/or injectable local anesthesia, and NSAIDs may enhance patient comfort.

[figure not shown]
[figure not shown]
[figure not shown]
[figure not shown]
[figure not shown]
[figure not shown]
[figure not shown]
Endpoints

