- Measurement of submental fat diameter
- Reporting and recording adverse events
- Evaluation the patient satisfaction

Visit 6 (20 weeks±4 days) (In subjectswith 3 injections):

- Digital AP and lateral photography of the patient's neck
- Grading of submental fat based on SMF
- Measurement of submental fat diameter
- Reporting and recording adverse events
- Evaluation the patient satisfaction

Participants:

This study will be conducted in 20 eligible participants.

Early Termination Policy: The decision to terminate the study early, due to safety concerns or to protect patient health, will be made by the Principal Investigator (PI) or the sponsor, with mutual agreement from both parties.

Withdrawal of Subjects

- The patients were allowed and free to refuse to cooperate with the study and follow-up whenever they want, but the researchers try to collect the maximum information, including the reasons for leaving the study and, if possible, the final results of the treatment.
- If a patient missed 2 or more consecutively scheduled visits, he/she was dismissed from the study.
- Occurrence of any of the exclusion criteria
- Occurrence of serious adverse event (SAE).

Data Collection

All required data will be recorded on the (paper) CRFs for this study, which will be designed and provided by PI. The reason for any missing data will be explained. All entries must be in permanent, blue ink. Errors will have single lines drawn through them with the correct data, recorder's initials, and date entered above the error. All errors must remain legible. Erasure or obliteration of errors in the CRF or other permanent study records are strictly prohibited.

Statistical analysis:

For statistical analysis, we performed descriptive statistics (mean, standard deviation or median and range, frequency and percentages). The efficacy of the treatment was assessed by comparing the mean/median value of each parameter among visits, using the Paired Sample T-test or the nonparametric equivalent, Wilcoxon test. SPSS 24 statistical software was used for data analysis. The statistical significance level was defined as $p<0.05$.

Adverse Events

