Adverse Event (AE) is described as any medical event that occurs in patients participating in a study, which differs from the clinical manifestations of the underlying disease progression and does not necessarily have a causal relationship with the treatment used in the study. Clinical manifestations that will be reported as adverse events include any symptoms, signs (such as any abnormal laboratory results), or temporary illness related to the use of the product being studied, whether or not these effects are causally related to the product under study.

Very common adverse events of DCA include:

- Pain
- Edema
- Numbness, tingling,
- Swelling
- Bruising
- Redness of the skin (erythema)
- Itching

Common adverse events of DCA include:

- Injection site reaction
- Bleeding
- Pain and discomfort
- Flushing
- Change of skin color
- Nerve injury around the jaw
- Skin tightness
- Difficulties in swallowing (dysphagia)
- Feeling sick (nausea)
- Headache

Uncommon adverse events of DCA include:

- Unusual taste in the mouth

- Difficulties in speaking
- Hair loss (alopecia)
- Hives (urticarial)
- Skin sores (ulcer)
- Scar

Adverse events of DCA where the frequency is not known include (frequency cannot be estimated from the available data) :

- Reduced or abnormal sensation in the area of the mouth (e.g. lip, tongue)
- Reduced sense of touch or altered sensation in the cheek
- Tissue damage and cell-death (necrosis) around the treatment area
- Injury of blood vessels if injected accidentally into artery or vein

The medical conditions that existed prior to the start of the study are only considered as adverse events if they have worsened during the course of the study and cannot be attributed to the natural progression of the disease.

Serious Adverse Reaction (SAR) is described as a harmful response to an intervention and includes:

- result in death.
- pose a risk of death.
- require hospitalization.
- prolong the duration of hospitalization.
- cause persistent or significant disability.
- result in congenital anomalies or birth defects.
- require medical or surgical intervention to prevent permanent damage

Recording and Reporting of Adverse Events:

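### The withdrawal rule imports every exclusion criterion without limit, so as written it can withdraw subjects for an expected reaction to the study treatment

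*Protocol*

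**What the plan says.** Under Withdrawal of Subjects, the protocol lists "Occurrence of any of the exclusion criteria" as one ground for withdrawal. SAP Section 3 repeats the line. Neither document says which exclusion criteria continue to apply once a subject has been treated, and neither exempts effects of the study product.

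Three of the imported criteria matter most here (protocol, Exclusion Criteria; same list in SAP Section 3):

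- "Any inflammation, active infection, unhealed wound, or tissue scar at injection site"
- "Patients with a history of dysphagia"
- "Those using anticoagulants or NSAID or other medications that increase the risk of coagulation disorders within 7 days before injection"

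The protocol's Adverse Events section and SAP Section 4 list the known effects of deoxycholic acid. Erythema, swelling and edema are very common. Dysphagia and injection site reaction are common. Skin ulcer and scar are uncommon. Tissue necrosis is listed with unknown frequency. No percentages are given.

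On NSAIDs, the protocol's Warnings and Precautions state: "Use of ice/cold packs, topical and/or injectable local anesthesia, and NSAIDs may enhance patient comfort".

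The study enrols 20 participants, each receiving one to three injections. SMF grade, calliper measurement and adverse events are assessed 4 and 12 weeks after the last injection. SAP Section 5 rules out imputation, and no analysis set is defined.

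**The concern.** Entry criteria are written for people who have not yet been treated. Reused unchanged as on-study withdrawal criteria, some of them describe what the product itself may cause. A subject could then leave the study because of the treatment, and that is informative loss.

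Two things are at stake. The first is the response rate. With no imputation and no defined analysis set, a withdrawn subject may simply drop out of the denominator, and nothing ensures that those lost respond like those who stay. The second is safety follow-up. Safety is part of the primary objective, and a subject with an ulcer, scar or dysphagia is one whose course needs to be observed. The documents do not say whether withdrawal on this ground ends injections only or also ends assessments. The stated effort to collect final results is written for patients who themselves decline to continue.

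**Working it through.** **Step 1. Set the imported criteria beside the listed effects.** This part is a comparison of texts. The plan gives no figure to reproduce, since the sample size of 20 is stated without a derivation.

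| Exclusion criterion | Listed effect or other text | Strength of the match |
|---|---|---|
| Tissue scar at the site | Scar (uncommon) | Direct, by name |
| Unhealed wound at the site | Ulcer (uncommon); necrosis (frequency unknown) | Direct in substance, different word |
| History of dysphagia | Dysphagia (common) | Only if occurrence is read to include new onset |
| Any inflammation at the site | Erythema, swelling, edema (very common) | By inference; inflammation is not itself a listed effect |
| NSAID within 7 days before injection | NSAIDs named as a comfort measure | Conflict if the NSAID is taken within that window before a session; the protocol gives no timing for comfort use |

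The firmest matches are with the less frequent effects. The match with the very common effects is the weakest.

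**Step 2. How often might this happen?** Let q be the share of subjects who meet an imported criterion because of treatment. The documents give no value, so q is an assumption. With N = 20 and independent subjects, expected withdrawals are 20q and P(at least one) = 1 − (1 − q)^20.

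| q (assumed) | Expected withdrawals | P(at least one) |
|---|---|---|
| 1% | 0.2 | 0.18 |
| 5% | 1 | 0.64 |
| 10% | 2 | 0.88 |
| 20% | 4 | 0.99 |

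**Step 3. What would the losses do to the response rate?** Each subject is 1/20 = 5 percentage points. For illustration take a true result of 14/20 = 70%. The 70% is the one-grade improvement figure quoted in the protocol's Introduction from a background study and is not a design assumption of this trial. Suppose k subjects are withdrawn, have no later SMF grade and are dropped from the denominator. The observed rate then lies between (14 − k)/(20 − k), if all k were responders, and 14/(20 − k), if all k were non-responders (valid for k up to 6, the number of non-responders).

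| k | Lowest | Highest |
|---|---|---|
| 1 | 13/19 = 68.4% | 14/19 = 73.7% |
| 2 | 12/18 = 66.7% | 14/18 = 77.8% |
| 4 | 10/16 = 62.5% | 14/16 = 87.5% |

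With four losses the shift runs from 62.5 − 70 = −7.5 points to 87.5 − 70 = +17.5 points. For comparison, the exact 95% interval for 14/20 is 45.7% to 88.1%. The possible bias is smaller than that sampling uncertainty, but no confidence interval would reveal it.

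**Step 4. Do the scheduled visits already cover these subjects?** Injections fall on day 1, week 4 and week 8. Four and 12 weeks after the last injection are therefore weeks 4 and 12 after one injection, weeks 8 and 16 after two, and weeks 12 and 20 after three. All are in the Study Timeline, so a subject who stops injections early can be assessed without new visits.

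**The case against.** The strongest reply is that exclusion criteria are entry criteria. Eligibility control is scheduled at Visit 0 only, and no later re-check is planned. That does not dispose of the point, because the withdrawal line exists to carry the criteria past entry, and occurrence refers to something that arises on study.

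A second reply is that carry-over may be a deliberate safeguard. The Introduction calls the drug contraindicated with a history of dysphagia. This stands as a reason not to tell the sponsor which reactions should count. It does not explain why follow-up should end as well.

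A third reply is that results may still be collected, since the first withdrawal bullet has researchers seek final results where possible. That bullet concerns patients who decline to continue, so it is only a partial answer.

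Some stronger inferences are not supported:

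- A reader might argue that "Any previous interventions to treat SMF" is met by every subject after the first injection. In a plan with up to three sessions, and with eligibility checked at screening, the natural meaning is interventions before the study.
- A reader might expect mass withdrawal on day 1 from redness or swelling. That needs these signs to be equated with inflammation, a criteria check that is not scheduled, and event rates that the documents do not give.
- A reader might call the withdrawal rule and the adverse event section contradictory. They are not: an event can be recorded and graded and the subject then withdrawn. What may be lost is later observation.
- Nothing in the documents shows that local reaction goes with response, so the direction of any bias is unknown.

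**Conclusion.** The point holds in this form: the rule, as written in both documents, can withdraw subjects for an expected reaction to treatment. It does not withdraw them merely for having been treated. The overlap is firm for scar and for ulcer or necrosis, depends on reading for dysphagia, and is inferential for erythema and swelling. The NSAID passages in the protocol also need to be reconciled with each other.

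How many subjects would be affected cannot be derived from the documents. At an assumed 5% to 10% of subjects, one or two withdrawals would be expected. The range of 62.5% to 87.5% for four losses rests on a true result of 14/20, on no SMF grade after withdrawal, and on analysis of the remaining subjects only. It gives bounds and does not predict bias of that size. In a single-arm study of 20 with no imputation, the exposure is worth removing because removing it costs little.

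**What to change.** Reconcile the protocol's Exclusion Criteria, Warnings and Precautions, Withdrawal of Subjects and Adverse Events sections with the matching text in SAP Sections 3 and 4:

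1. Replace the blanket reference with an explicit list of the exclusion criteria that apply after enrolment, including how NSAID use is to be handled. What goes on the list is the sponsor's clinical decision, and no view is taken on it here.
2. Separate stopping injections from leaving the study.
3. State that any subject who meets this ground remains, unless consent is withdrawn, in the already scheduled SMF, calliper and adverse event assessments, and is included in the analysis.

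The cost is about a paragraph in each document and a few more follow-up assessments in subjects who would otherwise have left. No new visits or procedures are needed.

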All adverse events and adverse drug reactions will be recorded in the patient's medical file as well as in the designated section of the CRF. They will be classified based on severity, relevance, and relation to the treatment used in the study, and in accordance with the investigator's criteria and the guidelines outlined below.

Classification of adverse events based on severity:

Adverse events will be classified according to their severity into three categories: mild [1], moderate [2], and severe [3], based on the following definitions:

Mild: Any reaction, sign, or symptom that the individual can recognize but does not influence performance or functioning.

Moderate: Any reaction, sign, or symptom(s) of a sufficient severity to make the subject uncomfortable. Performance of daily activities is influenced. This may require medical intervention.

Severe: Any reaction, sign, or symptom(s) of a sufficient severity to cause the subject severe discomfort. Performance of daily activities/functioning is compromised and causes disability and/or poses a specific risk to health. This usually requires medical intervention..

Note: Severe AEs are not necessarily serious unless one of the serious outcomes has occurred.

Classification of Adverse Events Based on Association with the Treatment Used in the Study: To determine the association between an adverse event or adverse drug reaction and the treatment used in the study, the following definitions will be considered:

-Certain: A clinical event involving changes in laboratory tests that are associated with a timely logical change in drug administration, and its occurrence cannot be explained by the person's current illness or other medications and substances. The response to drug reduction (dechallenge) should be clinically acceptable. This should be done from a pharmacological point of view and, if necessary, the drug re-exposure information (rechallenge) should be used .

-Probable: A clinical event involving changes in laboratory tests that are associated with a timely logical change in drug administration, and it is unlikely to be associated with a person's current illness or other medications and substances, and a reasonable clinical response is observed when the dose is reduced. There is no need for a rechallenge to put an undesirable event in this group.

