-Possible: A clinical event involving changes in laboratory tests that are associated with a timely logical change in drug administration, but it can be justified by the person's current illness or other medications and substances. Drug reduction information maybe not available or may be ambiguous.

Unlikely: A clinical event involving changes in laboratory tests that are associated with a timely logical change in drug administration, and it is acceptable to justify its occurrence through current illness of the individual or other drugs and substances.

Conditional/Unclassified: A clinical event involving changes in laboratory tests, which is declared as an adverse reaction and it is necessary to obtain more data or more data are being evaluated for its correct evaluation.

Unassessable/Unclassifiable: A symptom that is probably an adverse reaction, but because the information about it is insufficient or inconsistent and related data cannot be confirmed or completed, it cannot be judged.

Quality Assurance:

This study and the accuracy of the tests at intervals were evaluated by [name]; the quality assurance manager based on the relevant SOPs.

Accordance with GCP:

The study was conducted according to the principles provided by Good Clinical Practice (GCP) and the Declaration of Helsinki

References:

1. ASDS Consumer Survey on Cosmetic Dermatologic Procedures. 2018; Available at: <https://www.asds.net/Medical-Professionals/> Practice-Resources/ASDS-Consumer-Survey-on-Cosmetic Dermatologic- Procedures. Accessed
2. Liu, Michael, Cameron Chesnut, and Gary Lask. "Overview of Kybella (deoxycholic acid injection) as a fat resorption product for submental fat." *Facial Plastic Surgery* 35.03 (2019): 274-277.
3. <https://www.fda.gov/drugs/drug-approvals-and-databases/drug-trials-snapshots-kybella>

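### The causality scale does not separate Possible from Unlikely, and its dose-reduction and laboratory wording does not fit a fixed-dose injection study without laboratory tests

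*Protocol*

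**What the plan says.** The Protocol section on classifying adverse events by association with treatment defines six categories. The four main ones, *Certain*, *Probable*, *Possible* and *Unlikely*, all open with the same timing clause, which ties the event to a change in drug administration.

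- *Certain* rules out other explanations and adds: "The response to drug reduction (dechallenge) should be clinically acceptable".
- *Probable* asks that "it is unlikely to be associated with a person's current illness or other medications and substances" and that "a reasonable clinical response is observed when the dose is reduced".
- *Possible* applies when illness or other drugs can account for the event, and adds: "Drug reduction information maybe not available or may be ambiguous".
- *Unlikely* applies when "it is acceptable to justify its occurrence through current illness of the individual or other drugs and substances".

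The other two, *Conditional* and *Unassessable*, are for events awaiting more data or with inadequate information. Every category from *Certain* to *Conditional* describes the event as involving laboratory changes.

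The Protocol's Intervention section sets one to three sessions at least four weeks apart, each "with 2 ml of Embella® injectable solution, which contains 20 mg of DCA". What varies is whether another session is given: "If necessary, they will receive additional injections; otherwise, they will proceed with post-injection follow-up".

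The SAP's Safety Analysis also says events will be classified by relation to treatment and points to guidelines that follow. Only the severity definitions follow. Neither document says which categories count as related.

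**The concern.** A causality scale should give two raters with the same facts the same answer, and should have a place for the reaction the product most often causes. As printed, this scale may do neither. Its two lower categories appear to share their conditions, and its two upper ones depend on an observation the dosing plan does not generate.

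Safety is named in the primary objective, and the study has one arm of 20 participants. With no control group to show the background rate of events, the investigator's causality rating is the only attribution tool the documents offer.

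**Working it through.** No arithmetic applies. The documents give no related-event rate, agreement figure or cut-off to reproduce. The check sets the definitions side by side and then applies them to concrete events under the stated dosing.

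| Category | Timing plausible | Other cause | Response to dose reduction |
|---|---|---|---|
| Certain | required | excluded | called for |
| Probable | required | unlikely | required |
| Possible | required | plausible | may be missing or unclear |
| Unlikely | required | plausible | not mentioned |

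**Step 1: Possible against Unlikely.** The first two conditions match. The third entry for *Possible* is permissive: information on drug reduction may be absent or unclear, but nothing is excluded if it is present. *Unlikely* is silent on it. Every event meeting one definition therefore meets the other. For example, numbness is among the very common events listed, and the Protocol allows local anaesthesia at injection. Numbness after an injection given with a local anaesthetic has plausible timing and another drug as an explanation, so it fits both.

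**Step 2: implausible timing.** All four categories require plausible timing, *Unlikely* included. An event whose timing argues against a link has no main category.

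**Step 3: bruising after a single session, with no other cause.**

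- *Certain* and *Probable*: the timing and other-cause conditions are met, but there was no dose reduction to respond to.
- *Possible* and *Unlikely*: both fail, because each needs another explanation.

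The event meets none of the four. If it is well documented, it does not naturally belong in *Conditional* or *Unassessable* either.

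**Step 4: the same bruise when a later session is withheld.** This could be read as a form of dechallenge, but the Protocol does not say so. After a subject's last injection nothing remains to withhold.

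**Step 5: laboratory wording.** The visit schedule, which is the same in both documents, lists photography, fat measurement, physician grading, satisfaction, pain and adverse events. It lists no laboratory test, so the laboratory phrase in five of the six definitions has no scheduled data behind it.

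**Step 6: where the rating is used.** The adverse-event endpoint is graded by severity. The definition of an adverse event covers events whether or not the product caused them. Withdrawal after a serious event carries no relatedness condition, and early termination rests on safety concerns agreed between the principal investigator and the sponsor. No table, rate or test of related events is specified.

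**The case against.** The strongest reply is that literal reading is being applied selectively. If the laboratory phrase is strict, no bruise fits any category from *Certain* to *Conditional*, and the other arguments become moot. If it is read sensibly, the dose-reduction clause deserves the same latitude. The clause in *Certain* is softly worded, a later session can be withheld, and classification also follows the investigator's own criteria. Part of this stands: the dose-reduction problem shrinks for a rater who reads generously. The overlap in Step 1 does not, because it depends on neither clause. The investigator's criteria are not written down, so they cannot be relied on to separate the categories.

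The second reply is that little depends on the rating. This stands and limits the point, as Step 6 shows. A reader might infer that the trial's count of related events is irreproducible, or that the related share could lie anywhere from 0 to 100%. The documents do not support that as a finding. No such count is planned, no agreement data exist, and the range is only a logical bound on a subset of unknown size. It also assumes that *Possible* counts as related and *Unlikely* does not. The exclusions for local inflammation, active infection and recent anticoagulant or NSAID use may keep that subset small, although permitted anaesthesia means it need not be empty.

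**Conclusion.** The scale is wrong as written, to a minor-to-moderate degree. *Possible* and *Unlikely* are not distinguishable from their text, none of the four main categories accommodates implausible timing, and the dose-reduction and laboratory wording does not match this study's dosing or schedule. Only the relation-to-treatment classification is affected, and the size of the effect cannot be computed from the documents.

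The finding that an ordinary injection-site reaction fits none of the four main categories rests on two assumptions: that the dose-reduction clause is applied literally, and that withholding a session does not count as reduction.

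Two stronger readings should be resisted. A reader might infer that such reactions cannot be rated above *Possible*; in fact, with no other cause, they fail *Possible* as well. A reader might also infer that the safety objective as a whole is compromised; reporting of all events by severity does not depend on this scale.

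**What to change.** Four wording changes, none of which touches dosing, visits or sample size:

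1. Define *Unlikely* by timing that makes a link improbable, so that it excludes *Possible*.
2. In *Certain* and *Probable*, replace the dose-reduction condition with timing, location and course after the injection, and no other likely cause.
3. Write *including* rather than *involving* for laboratory changes.
4. State in the SAP which categories count as related, if a related-event summary is to be reported.

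The cost is an edit to both documents and a short CRF guide. More events may be rated as related. Parts of the Protocol are written in the past tense, so some ratings may already exist; those would have to be redone under the revised definitions.
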